  - 6 Subjects with open epiphyseal growth plates at the most recent assessment will undergo knee (A/P) and hand/wrist radiographs (P/A view) and measurements of linear and knee height (in triplicate) at Amendment 3 Screening and/or Non-flare-up Day 1. As the linear growth assessments cannot be performed remotely, all assessments scheduled at these time points will be performed at the clinical site. Subjects for whom radiographs were performed within the last 3 months will not need to repeat radiographs at Screening. Subjects with open epiphyseal growth plates at this assessment will also be evaluated at Months 6, 12, 18, 24, 30, 36, 42 and 48. Limb/joint AEs in these subjects will be evaluated by clinical and radiographic assessments deemed appropriate by the Investigator. Once a subject has achieved 100% skeletal maturity (confirmed by radiography), knee and hand/wrist radiographs will no longer be required. If 100% skeletal maturity is not achieved at both locations, then only the location that is still maturing would need to be monitored. In addition, once a subject is 18 years old, linear growth assessments in triplicate and knee height will no longer be required.
  - 7 These additional knee and hand/wrist radiograph assessments will be performed every 3 months ( $\pm 2$  weeks) in those subjects who (1) received flare-up dosing in the period of time since their last assessment; and (2) had not achieved 100% skeletal maturity on their last assessment. Radiographic assessments required because of flare-up status at the time of a remote visit will instead be conducted at the clinical site unless the Investigator determines they can be performed at a local medical facility. All remote assessments will be performed at the clinical site if the radiographs cannot be performed locally.
  - 8 ECG may be performed at the subject's home by qualified study personnel, at a local medical facility, or at the clinical site.
  - 9 Continuous non-flare-up-based treatment unless flare-up-based treatment is initiated.
  - 10 Analysis of samples can be completed at a local, qualified laboratory. The investigative site should notify the study team if the local laboratory cannot test all the analytes listed in Table 6. If the total thyroxine (Total T4), free T4, uric acid, gamma glutamyl transferase, inorganic phosphorous, very low-density lipoprotein, or globulin parameters are not available through the local laboratory, and alternative arrangements cannot be made, testing of these analytes may be omitted provided other subject-assessments of thyroid function (ie, thyroid-stimulating hormone), lipid metabolism (ie, triglycerides, low-density lipoprotein, high-density lipoprotein, and total cholesterol), and protein metabolism (ie, total protein and albumin) are available and confirmed to be stable as per the Investigator. Alternative arrangements to test the listed analytes are to be made if the Investigator, Medical Monitor, or sponsor determines that they have the potential to impact subject safety. In the event the local laboratory is unable to test any other analytes, they may be omitted in exceptional circumstances after consultation with the sponsor. Such exceptions will not be applied to any of the key safety analytes (see Section 7.2.6).
  - 11 If urinalysis results are abnormal, then a microscopic evaluation will be completed.
  - 12 Pregnancy testing will be performed monthly for females of child-bearing potential. Urine pregnancy test will be performed only when a serum pregnancy test is not obtained.
  - 13 Age-appropriate versions of the FOP-PFQ and PROMIS Global Health Scale will be used.
  - 14 CAJIS assessment may be performed remotely or by videoconferencing.
  - 15 Baseline for low-dose WBCT scan, excluding head, will be at Amendment 3 Screening (ie, when the subject provides informed consent/assent for Amendment 3). The low-dose WBCT scans, excluding head, will only be performed during annual visits (not at the 6-month visit).
  - 16 Blood samples for pharmacokinetic assessment of non-flare-up dosing will be collected at the first 3-month safety assessment at predose and 3, 6, 10, and 24 hours post-dose; if samples cannot be obtained during the first 3-month safety assessment, or if the subject is on flare-up-based treatment, then the blood sample for non-flare-up-based treatment pharmacokinetics can be obtained during any subsequent 3-month safety visit.

Note: study procedures that require sedation will not be performed.

AE = adverse event, A/P = anterior/posterior, CAJIS = Cumulative Analogue Joint Involvement Scale for FOP, C-SSRS = Columbia Suicide Severity Rating Scale, EOS = end of study, EOT = end of treatment, FOP-PFQ = Fibrodysplasia Ossificans Progressiva physical function questionnaire, P/A = posterior/anterior; PK = pharmacokinetic(s), PROMIS = Patient Reported Outcomes Measurement Information System, WBCT = whole body computed tomography.

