Study Design	
A Phase 2, single-center, open-label study that will explore different dosing regimens of palovarotene in adult and pediatric subjects with FOP. References to Parts B/C/D are to PVO-1A-202 Parts B/C/D which corresponds to PVO-1A-204, ongoing in France.
 
Under the original protocol and Amendment 1, subjects who successfully completed Study PVO-1A-201 as well as up to two new adult subjects were followed for up to 24 months. Subjects who participated under Amendment 1 will be followed for up to an additional 48 months. No new subjects will be enrolled.
 
Non-Flare-up Based Treatment
 
All subjects will receive non-flare-up based treatment of 5 mg palovarotene once daily (weight-adjusted doses for skeletally immature subjects [see table below and Table 5]). Note: all weight-based dosing, both non-flare-up-based and flare-up, will cease when subjects become skeletally mature, but radiographic assessment of the growth plate (performed every 6 months) will continue until these subjects achieve 100% skeletal maturity as defined as growth plate closure at both knee and hand/wrist locations.
 
Additional radiographic assessments will be performed every 3 months in those subjects who (1) received the flare-up dosing regimen in the period of time since their last radiographic assessment; and (2) had not achieved 100% skeletal maturity on their last radiographic assessment.
 
Subjects will follow all assessments as outlined in Table 1, Table 2 and Table 3. Subjects who cannot receive non-flare-up based treatment will only undergo annual assessments (clinical laboratory tests will not be performed). In the event of a flare-up, these subjects will receive flare-up-based treatment and undergo all flare-up based assessments, including clinical laboratory tests and radiographs if they have not reached 100% skeletal maturity.

---

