Study Population of Subjects Starting Non-Flare-up-based Treatment During Amendment 3	
Inclusion Criteria
 
 
1. Subjects must be accessible for treatment with palovarotene and follow-up. Subjects living at distant locations from the investigational site must be able and willing to travel to a site for the initial and all on-site follow-up visits.
 
2. Subjects must be able to undergo low-dose WBCT scan, excluding head.
 
 
Exclusion Criteria
 
 
1. Amylase or lipase >2x above the upper limit of normal (ULN) or with a history of chronic pancreatitis.
 
2. Elevated aspartate aminotransferase (AST) or alanine aminotransferase (ALT) >2.5x ULN.
 
3. Fasting triglycerides >400 mg/dL with or without therapy.
 
4. Subjects experiencing suicidal ideation (type 4 or 5) or any suicidal behavior within the past month as defined by the Columbia Suicide Severity Rating Scale (C-SSRS).
 

Investigational Product	
Palovarotene supplied as powder-filled hard gelatin capsules. The capsules may be swallowed whole or opened and the contents added onto specific food: apple sauce, pudding, or yogurt.

Dose/Route/Regimen for Non-Flare-Up Based Treatment	
Palovarotene: 5 mg daily or weight-based equivalent for skeletally immature subjects (upon entry into the study) / taken orally with food / at approximately the same time each day. For 5 mg palovarotene, weight equivalent doses for 20 to <40 kg, 40 to <60 kg, and ≥60 kg will be 3 mg, 4 mg, and 5 mg, respectively.

**Dose/Route/Regimen for Flare-up-based Treatment** Palovarotene initiated at the start of a flare-up for subjects 18 years of age and older: 20 mg for 4 weeks (28 days) once daily, 10 mg for 8 Weeks (56 days) once daily for a total of 12 weeks (84 days) (may be extended in 4-week intervals if flare-up is ongoing and continue until flare-up resolves) / weight-adjusted for subjects under the age of 18 years / taken orally with food / at approximately the same time each day.  
The weight-adjusted palovarotene doses and dose de-escalation for flare-up and non-flare-up-based dosing are:

Weight range category	20-mg Equivalent	15-mg Equivalent*	10-mg Equivalent	7.5-mg Equivalent*	5-mg Equivalent*	2.5 mg Equivalent
20 to <40 kg	12.5 mg	10 mg	6 mg	4 mg	3 mg	1.5 mg
40 to <60 kg	15 mg	12.5 mg	7.5 mg	5 mg	4 mg	2 mg

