## **3 STUDY DESIGN**

### **3.1 Overview of the Study Design**

This is a Phase 2, single-center, open-label study that will explore different dosing regimens of palovarotene in adult and pediatric subjects with FOP. References to Parts B/C/D are to PVO-1A-202 Parts B/C/D which corresponds to PVO-1A-204, ongoing in France.

Under the original protocol and Amendment 1, subjects who successfully completed Study PVO-1A-201 as well as up to two new adult subjects were followed for up to 24 months.

Subjects who participated under Amendment 1 will be followed for up to an additional 48 months. No new subjects will be enrolled under this amendment.

All subjects will receive non-flare-up based treatment of 5 mg palovarotene once daily (weight-adjusted doses for skeletally immature subjects). Note: all weight-based dosing will cease when subjects become skeletally mature, but radiographic assessment of the growth plate will continue until these subjects achieve 100% skeletal maturity at both knee and hand/wrist locations performed at Months 6, 12, 18, 24, 30, 36, 42, 48, 54, 60 and 72. Additional radiographic assessments will be performed at Months 3, 9, 15, 21, 27, 33, 39, 45, 51, 57, 63, 66, or 69 in those subjects who (1) received the flare up dosing regimen in the period of time since their last radiographic assessment; and (2) had not achieved 100% skeletal maturity on their last radiographic assessment.

Subjects will follow all assessments as outlined in Table 1 and Table 2. Adult subjects who cannot receive non-flare-up based treatment will only undergo annual assessments (clinical laboratory tests will not be performed). In the event of a flare-up or traumatic event, these subjects will receive flare-up-based treatment and undergo all flare-up-based assessments, including clinical laboratory tests and radiographs if they have not reached 100% skeletal maturity.

Adverse events will be assessed at every site and remote visit during both non-flare-up based and flare-up-based treatment. In case of early termination or withdrawal of a subject, every reasonable effort will be made by the study staff to have the subject return to the site in order to complete all end of treatment (EOT) and end of study (EOS) evaluations.

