**Flare-Up Based Treatment**

Subjects and/or their parents/caregivers will report potential flare-up symptoms to site personnel; such symptoms include, but are not limited to, pain, swelling, redness, decreased range of motion, stiffness, and warmth. Only one symptom is required to define a flare-up. If these symptoms are consistent with previous flare-ups, include a subject-reported onset date, and are confirmed by the Investigator as associated with a flare-up, subjects will immediately receive open-label palovarotene treatment as follows:

- 20 mg for 4 weeks (28 days) once daily. The first dose will be taken upon flare-up confirmation by the Investigator. To be followed by:
- 10 mg for 8 weeks (56 days) once daily, for a total flare-up treatment duration of 12 weeks (84 days); 10 mg treatment may be extended if the flare-up is ongoing and continue until the flare-up resolves. Dosing will be extended in 4-week intervals and be based on clinical signs and symptoms as assessed by the Investigator.

Subjects under the age of 18 years will receive weight-adjusted doses of 20 mg palovarotene (for 28 days) and 10 mg palovarotene (for 56 days) as shown in Table 5. (Note: all weight-based flare-up dosing will cease when subjects are 18 years old, but radiographic assessment of the growth plate will continue until these subjects achieve 100% skeletal maturity at both knee and hand/wrist locations.)

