Flare-Up Cycle Safety Day 1 is defined as the first day that study drug is administered for the first flare-up or traumatic event during that cycle. Safety assessments will be performed on Flare-up cycle Safety Day 1 and every 12 weeks thereafter until treatment of the last flare-up or traumatic event in the flare-up cycle is completed. If any flare-up in a cycle has not resolved after 12 weeks, treatment and safety assessments will be extended and 10 mg palovarotene (or the weight-based equivalent) will be administered in 4-week intervals until all the flare-ups resolve and flare-up-based treatment has been completed. It is possible that subjects may experience more than one Flare-up Cycle during the study.

Subjects receiving flare-up-based treatment will follow all procedures and undergo all assessments as specified in the Schedule of Assessments in Table 3. All assessments will occur remotely, unless the Investigator deems it necessary to evaluate subjects at the clinical site.

Once all flare-ups or traumatic events in a cycle have resolved and flare-up based treatment has been completed, subjects will resume non-flare-up based treatment with 5 mg palovarotene once daily (weight-adjusted doses for skeletally immature subjects as shown in Table 5).

Pharmacokinetics of palovarotene dosing will be assessed twice during flare-up based treatment: once during the 20-mg regimen at any time between Study Days 4 to 28, and once during the 10- mg regimen at any time between Study Days 32 to 84, for the first treated flare-up only. If this is not possible for the first treated flare-up, pharmacokinetics blood samples can be obtained during any subsequent flare-up dosing cycle. Pharmacokinetic blood samples will be collected at pre-dose and 3, 6, 10, and 24 hours post-dose. Subjects who underwent a prior flare-up pharmacokinetic assessment will not have flare-up treatment pharmacokinetics

assessed again. However, these subjects will require a pharmacokinetic assessment during non-flare-up palovarotene treatment at a 3-month safety assessment (see Section 7.5).

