- **Flare-up dosing regimen:** The rationale for increasing the non-flare-up-based palovarotene dose at the time of a flare-up comes from both the animal pharmacology and available clinical trial results. The nonclinical data from two different mouse models of FOP demonstrated a dose-related decrease in HO volume; and suggested that flare-up-based treatment using an HED of 20 mg may be necessary to optimally prevent HO following an injury (equivalent to a flare-up in humans). The Phase 2 program has evaluated four different palovarotene dosing regimens, three flare-up based episodic treatment regimens and one non-flare-up-based/flare-up regimen. Preliminary clinical data on 103 prospectively assessed flare-ups demonstrated an approximate 45% reduction in the proportion of flare-ups with new HO, and an approximate 75% decrease in new HO volume, in those flare-ups treated with palovarotene 10/5 mg over 6 weeks compared to placebo/untreated flare-ups; and an approximate 65% reduction in proportion of flare-ups with new HO and an approximate 98% reduction in HO volume in those flare-ups treated with the non-flare-up-based/flare-up regimen 20/10 mg over 12 weeks (the regimen in the current study) compared to placebo/untreated flare-ups. These data provide a strong rationale for the continued evaluation of palovarotene as a potential treatment of FOP, and the selection of non-flare-up-based daily administration of 5 mg palovarotene, with dose escalation to 20 mg once daily for 4 weeks followed by 10 mg for 8 weeks (with treatment extension possible per Investigator discretion for persistent flare-ups) for all subjects. The flare-up dosage will be adjusted for weight in subjects under the age of 18 years.
- While it is recognized that flare-ups can occur in the absence of any apparent causative factor, there is a high risk that substantial traumatic events such as surgery, intramuscular immunizations, mandibular blocks for dental work, muscle fatigue, blunt muscle trauma from bumps, bruises, falls, or influenza-like viral illnesses can induce flare-ups and progressive HO formation. In one survey of FOP patients, flare-ups were induced in two-thirds of falls and resulted in permanent loss of movement in 93% of patients. Thus, subjects experiencing substantial high-risk traumatic events that the Investigators deem likely to lead to a flare-up will be treated with the flare-up regimen.

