### **6.4 Administration**

All subjects will receive non-flare-up based treatment of 5 mg palovarotene once daily (weight-adjusted doses for skeletally immature subjects). The first day that subjects receive non-flare-up based treatment will be Non-Flare-Up Day 1. Details for handling, preparing, storing, and discarding study drug will be provided to subjects.

Subjects who began non-flare-up based treatment under Amendment 1 will continue this visit schedule, and will receive non-flare-up based treatment for up to an additional 48 months.

Subjects who will start non-flare-up based treatment will receive non-flare-up based treatment for up to 48 months. Subjects who cannot receive non-flare-up based treatment will only undergo annual assessments (clinical laboratory tests will not be performed). In the event of a flare-up, these subjects will receive flare-up-based treatment and undergo all flare-up based assessments, including clinical laboratory tests.

Flare-up based treatment can begin immediately after the Investigator confirms the presence of a flare-up or the presence of a substantial high-risk traumatic event likely to lead to a flare-up.

Subjects with normal or non-clinically significant abnormal safety laboratory results observed within 1 month of flare-up based treatment will not need to have laboratory tests performed at Flare-up Day 1. The Investigator will determine whether subjects with clinically significant abnormal laboratory results in the most recent assessment will need to be re-assessed prior to beginning flare-up based treatment. The only exception is for pregnancy testing, which must be performed monthly. For subjects receiving flare-up based treatment, Flare-up Day 1 is defined as the first day that flare-up based treatment with study drug is administered.

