Subjects will report potential flare-up symptoms or traumatic events to site personnel, and if confirmed by the Investigator as associated with a flare-up or, in the case of trauma, likely to lead to a flare-up, subjects will immediately begin flare-up based treatment with palovarotene 20 mg for 4 weeks (28 days) once daily followed by palovarotene 10 mg for 8 weeks (56 days) once daily (or weight-based equivalent), for a total duration of 12 weeks (84 days). Based on clinical signs and symptoms as determined by the Investigator, treatment may be extended in 4-week intervals while on-treatment with 10 mg palovarotene, and continue until the flare-up resolves and 4-week extension treatment has been completed. Flare-up dosing will be weight-adjusted for subjects under the age of 18 years (Section 3.1). Subjects will be provided with the appropriate dose of study drug to be used to initiate treatment with palovarotene when a flare-up or traumatic event is confirmed by the Investigator. Should a subject experience a new intercurrent flare-up or traumatic event at any time during flare-up based treatment, the 12-week dosing regimen will restart upon confirmation by the Investigator (ie, 4 weeks of 20 mg palovarotene followed by 8 weeks of 10 mg palovarotene [or weight-based equivalent]).

Once all flare-ups or traumatic events in a cycle have resolved and flare-up based treatment has been completed, subjects will resume non-flare-up based treatment with 5 mg palovarotene once daily (weight-adjusted doses for skeletally immature subjects).

The dose of study drug taken each day will be documented in the subject dosing diary.

Many FOP patients experience difficulty swallowing intact capsules or tablets due to ankylosis of the jaw. In order to facilitate drug administration, subjects or caregivers may sprinkle the contents of the capsule onto specific foods as specified in the dosing instructions. Subjects should be instructed to take study drug orally following a full meal at approximately the same time each day and to avoid foods that are known to induce or inhibit the activity of the CYP3A4 enzyme (eg, grapefruit, pomelo, or juices containing these fruits). Due to the potential for dermal absorption of study drug, subjects and caregivers will be instructed to wear protective gloves when handling the study drug capsule.

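### PVO-1A-204 gives two stopping rules for weight-adjusted flare-up dosing, so a skeletally mature 14- to 17-year-old under 60 kg has two specified doses

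*Protocol*

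**What the plan says.** All places are in the PVO-1A-204 protocol (Amendment 6) unless PVO-1A-202 is named.

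**Maturity rule**
- Synopsis, Study Design, Non-Flare-up Based Treatment: "all weight-based dosing, both non-flare-up-based and flare-up, will cease when subjects become skeletally mature". No percentage is given. Growth-plate radiographs continue after that point until 100% maturity.
- Section 3.1, overview: "all weight-based dosing will cease when subjects become skeletally mature". Flare-up dosing is not named, but the statement is not limited to non-flare-up dosing either.

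**Age rule, in the flare-up text**
- Synopsis, Flare-Up Based Treatment, and Section 3.1, Flare-Up Based Treatment: "all weight-based flare-up dosing will cease when subjects are 18 years old" (same words in both).
- Synopsis, Dose/Route/Regimen for Flare-up-based Treatment: "weight-adjusted for subjects under the age of 18 years / taken orally with food".
- Section 3.3: "The flare-up dosage will be adjusted for weight in subjects under the age of 18 years".
- Section 6.4: "Flare-up dosing will be weight-adjusted for subjects under the age of 18 years (Section 3.1".

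For the 5 mg daily dose, Section 6.4 uses maturity: "All subjects will receive non-flare-up based treatment of 5 mg palovarotene once daily (weight-adjusted doses for skeletally immature subjects". The return to 5 mg after a flare-up, in Section 3.1, does likewise.

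**The concern.** Age and skeletal maturity are different criteria, and the protocol itself expects them to diverge. Children under 14 are off drug and will not restart (Section 3.1). Section 7.7, item 4(c), describes subjects aged 14 and older as having reached at least 90% skeletal maturity. A subject aged 14 to 17 can therefore be mature for the synopsis note and still a minor for the flare-up text. The first gives the full dose and the second the weight-adjusted dose.

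What is at stake is the dose given to an individual minor. Flare-up treatment starts as soon as the investigator confirms the event (Section 6.4), so the rule has to be settled beforehand. Section 9.2.6 asks for the protocol to be followed exactly, and for such a subject both instructions cannot be.

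**Working it through.** The plan states no figure to reproduce, so the check sets the two rules side by side and applies Table 5.

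**Inputs**
- Regimen (Section 3.1): 28 days at the 20-mg level, then 56 days at the 10-mg level, 84 days in all.
- Table 5, 20-mg and 10-mg equivalents: 12.5 and 6 mg at 20 to <40 kg; 15 and 7.5 mg at 40 to <60 kg; 20 and 10 mg at 60 kg or more.

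**Formula**

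Course total = 28 × high dose + 56 × low dose.

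**Results**
- Full dose: 28 × 20 + 56 × 10 = 560 + 560 = 1120 mg.
- 40 to <60 kg, adjusted: 28 × 15 + 56 × 7.5 = 420 + 420 = 840 mg. Ratio 1120/840 = 1.333, so the full dose is 33.3% higher.
- 20 to <40 kg, adjusted: 28 × 12.5 + 56 × 6 = 350 + 336 = 686 mg. Ratio 1120/686 = 1.633, so the full dose is 63.3% higher.
- 60 kg or more: 28 × 20 + 56 × 10 = 1120 mg under both rules.

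**Which dose each rule gives**

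| Subject under 60 kg | Maturity rule | Age-18 rule |
|---|---|---|
| 14 to 17, not mature | adjusted | adjusted |
| 14 to 17, mature | full | adjusted |
| 18 or older, mature | full | full |
| 18 or older, not mature | adjusted, by implication only | full |

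The second row is the explicit conflict. The fourth is weaker: the synopsis note is a stopping rule, and it does not clearly grant an adjusted flare-up dose to anyone aged 18 or older.

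**Threshold**

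The synopsis note cannot mean 100% maturity, because it continues radiographs from that point until 100%. About 90% is a reasonable reading, since that figure appears elsewhere in PVO-1A-204 and sets the dosing rule in PVO-1A-202. That is an assumption. It affects how many subjects fall in the second row, but not whether the two rules conflict.

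**The case against.** Four points can be made against this.

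1. **The synopsis note sits under the non-flare-up heading.** A reader might take it as limited to the 5 mg dose. Its wording rules that out, because it names flare-up dosing expressly. The heading does not reconcile the texts.

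2. **The maturity rule may be the intended one.** The note closely follows the PVO-1A-202 synopsis, where weight-based dosing of both kinds ends at 90% maturity or more, and the PVO-1A-202 flare-up text (Section 3.1) is consistent with that. The Section 3.1 overview in PVO-1A-204 repeats the maturity rule. A reader might infer from five statements against one or two that the synopsis note is simply a slip. That is likely, because PVO-1A-204 otherwise uses maturity for the 5 mg dose and age for flare-up doses, but the documents do not prove it. The fix must therefore rest on the sponsor's confirmation.

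3. **The safety weight is limited.** Section 1.1.3.2.3 links the flare-up regimen to a higher risk of premature fusion in subjects with open growth plates, and a reader might infer that the full dose endangers this group. But Section 7.7, item 4(b), calls the risk of early closure low once maturity reaches at least 90%. Nor do the milligram differences show that the adjusted dose under-treats: Section 1.1.3.2.1 reports that the adjusted doses were simulated to give exposures within the adult range.

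4. **Few subjects, if any, are affected.** There is one site, approximately nine subjects and no further enrolment. An affected subject must be 14 to 17, mature, under 60 kg, on drug and treated for a flare-up or traumatic event.

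Points 2 to 4 stand as limits on the finding. None of them gives the affected subject a single specified dose.

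**Conclusion.** The contradiction holds in current PVO-1A-204 text and concerns a dosing rule. For a skeletally mature subject aged 14 to 17, the full dose exceeds the adjusted one by a nominal 280 mg per 84-day course at 40 to <60 kg (1120 − 840) or 434 mg at 20 to <40 kg (1120 − 686). At 60 kg or more there is no conflict.

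A reader might extend the point to subjects aged 18 or older who are still immature. The text only implies a second dose for them and does not identify any such subject below the dosing threshold. The radiographs that continue past 18 run to 100% maturity, so they do not show one.

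Some subjects aged 14 or older may be below 90% maturity, as Section 7.7, item 2(d), allows. For those under 18 the two rules agree.

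The number affected is not shown and may be zero of about nine. No endpoint, analysis or statistical figure changes. The point is worth correcting because it sets a dose and the edit is small.

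**What to change.** The sponsor confirms which rule governs flare-up dosing and states it once.

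**Default.** Limit the synopsis note (Non-Flare-up Based Treatment) and the Section 3.1 overview to non-flare-up dosing. Age 18 then governs flare-up doses throughout. This changes two places, leaves all five flare-up statements, including Section 6.4, as they are, and gives the lower nominal dose in mature minors under 60 kg. Giving the maturity threshold in the same edit would be useful, though the contradiction does not require it.

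**If alignment with PVO-1A-202 was intended.** Change the five flare-up statements (two in the synopsis, and Sections 3.1, 3.3 and 6.4) to weight adjustment below 90% skeletal maturity, and put the same threshold in the synopsis note and the Section 3.1 overview. The amendment should say openly that, relative to the present flare-up text, this raises the nominal flare-up dose in mature minors under 60 kg by 33% or 63%.

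Neither route adds procedures or data. Both need regulatory and ethics approval, because Section 9.2.5 requires it for every protocol amendment and makes no exception for wording changes. The default can go into the next amendment.
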